2. RATIONALE, OBJECTIVES, AND BENEFIT-RISK ASSESSMENT

2.1. RATIONALE FOR PERFORMING THE TRIAL

This study seeks to investigate the potential benefit of the addition of adjuvant immunotherapy to IMRT based re-irradiation in RPA Class I and II patients with locoregional recurrent or second primary (RSP) head and neck squamous cancer. Our hypothesis is that nivolumab will lead to an improved disease control in this population at high risk of relapse which will translate into an improved 1 year progression-free survival (PFS) compared to the standard re-irradiation with IMRT. We also believe based on the recent PRO data presented at ESMO 2016, that nivolumab will preserve the quality of life in this heavily pre-treated patient population. Given these initial exciting results in patients with advanced head and neck squamous cancer, there is strong rationale for the addition of PD-1 inhibition to an IMRT re-irradiation backbone. This study explores this combination therapy against the standard IMRT re-irradiation with or without other systemic therapies used in the MIRI cohort.

2.2. TRIAL OBJECTIVES

2.2.1. Primary Objective

To assess the 1-year PFS for patients with recurrent or second primary head and neck squamous cancer treated with IMRT re-irradiation with concurrent and adjuvant nivolumab

2.2.3. Secondary Objectives

- 1- Evaluate the 1-yr OS of patients treated with re-irradiation and nivolumab
- 2- Evaluate patient QOL
- 3- Evaluate patterns of failure including local, regional and distant failure rates at 1yr
- 4- Identify and estimate the incidence rate of acute and late toxicities associated with combined re-irradiation and concurrent and adjuvant nivolumab

Exploratory Objectives:

To identify potential biomarkers related to clinical benefit to concurrent and adjuvant nivolumab and re-irradiation in patients with RSP HNSCC.

3. STUDY POPULATION

Number of Centers

Three sites will be involved.

Number of Participants

A total of 46 patients will need to be accrued in 2.5 years and followed for an additional 2 years (estimated maximum total of 51 patients). Accounting for a 20% drop out rate, 62 patients will need to be consented.

3.1. SELECTION OF STUDY POPULATION

Main Diagnosis for Study Entry

All patients included in this trial must be candidates for re-irradiation with IMRT

3.1.1. Inclusion Criteria

- 1- Patients with recurrent squamous cell carcinoma or a second primary arising in a previously irradiated field

- 2- Patients must be \geq 18 years of age.
- 3- Life expectancy of greater than 6 months.
- 4- Patients cannot have distant metastases and have to be candidates for curative re-irradiation
- 5- Patients with salivary gland tumors are excluded (patients with nasopharynx CA or sinonasal cancers can participate)
- 6- Patients with unresectable disease are eligible.
- 7- Patients who undergo surgical resection will be allowed regardless of HPV status provided they: have one of the following criteria: 1- Positive margins on pathology; 2- evidence of extracapsular spread on nodal pathology; 3- gross residual disease on postoperative or simulation imaging; 4 – N2/3 disease; 5 – T3/4 disease; 6 – multifocal perineural invasion and/or lymphovascular space invasion.
- 8- The majority of the anticipated target volume ($> 50\%$) must have been previously treated to ≥ 40 Gy; Prior RT must have been completed >6 months prior to initiation of IMRT reirradiation. If previous RT records are unavailable, investigators can estimate the dose to previously treated tissues based on completion notes or other treatment history.
- 9- An ECOG performance score 0-2 (see Appendix 1)
- 10- Granulocytes $>1500/\text{mm}^3$, platelets $>100,000/\text{mm}^3$, bilirubin $<1.5 \text{ mg/dl}$, creatinine $<1.5 \text{ mg/dl}$
- 11- No other concurrent invasive malignancies treated for the past year (localized prostate cancer or early stage skin cancer are not exclusion criteria);
- 12- Patients with carotid artery involvement or encasement will be allowed provided they have no symptoms related to carotid involvement;
- 13- No prior exposure to immunotherapy agents
- 14- Ability to understand and the willingness to sign a written informed consent document

3.1.2. Exclusion criteria:

- 1- Any known factors that would pose a contraindication to receiving nivolumab
- 2- RPA class III patients defined as those expected to begin reirradiation within 2 years of first course of radiation therapy AND are PEG dependent or have a tracheostomy (patients who have undergone total laryngectomy are not excluded)
- 3- Patients with metastases
- 4- Prior treatment with a PD-1/PD-L1 inhibitor.
- 5- Female patients of childbearing potential must have a negative serum pregnancy test within 7 days prior to enrollment.
- 6- Patients with primary salivary gland cancers are excluded.
- 7- Patients who have had chemotherapy or biological therapy within 4 weeks of registration.
- 8- Uncontrolled intercurrent illness including, but not limited to, ongoing or active infection, autoimmune disease requiring systemic steroids, symptomatic congestive heart failure, unstable angina pectoris, cardiac arrhythmia, or psychiatric illness/social situations that would limit compliance with study requirements.
- 9- Patients who are pregnant or breast-feeding
- 10- Patients with known active HIV, Hep B, or Hep C infection
- 11- Subjects with a condition requiring systemic treatment with either corticosteroids ($> 10 \text{ mg daily prednisone equivalents}$) or other immunosuppressive medications within 14 days of study drug administration. Inhaled or topical steroids and adrenal replacement doses $> 10 \text{ mg daily prednisone equivalents}$ are permitted in the absence of active autoimmune disease.

3.1.3. Discontinuation Criteria

Patients will be removed from study when any of the following criteria applies:

- Patients with grade 3 or 4 infusion reaction must not receive further treatment with nivolumab

- If radiotherapy is interrupted for > 3 consecutive weeks, patient's protocol treatment will be discontinued.
- Extraordinary Medical Circumstances: If at any time the constraints of this protocol are detrimental to the patient's health, the protocol treatment should be discontinued.
- Patients who develop progressive disease will be discontinued from the protocol therapy.
- Patients who develop unacceptable toxicity will be discontinued from the protocol therapy.
- Patients may withdraw consent and withdraw from the study at any time for any reason.

3.1.4. Premature Discontinuation of Patients from the Study

Those who discontinue protocol therapy early will be followed for response until progression and for survival for 2 years from the date of initiation of radiation. Patients removed from study for unacceptable adverse events will be followed until resolution or stabilization of the adverse event.

4. STUDY DESIGN AND TREATMENT

4.1 OVERALL TRIAL DESIGN AND PLAN

This will be a phase II single arm study of IMRT re-irradiation in combination with nivolumab in the concurrent and maintenance setting. IMRT based reirradiation must be used. VMAT and Cyberknife technologies will be allowed.

Treatment plan:

RT will be given as 60-66Gy in 30-33 once daily fractions. Nivolumab will be given 2 weeks prior to the initiation of IMRT (week -2), and every 2 weeks for 4 more doses during radiation (weeks 0, 2, 4, 6) (240 mg over 30-60 minutes IV each dose, for a total of 5 doses). After the completion of IMRT, nivolumab will be given on a q4wk schedule for an additional 10 treatments (480 mg over 30-60 minutes IV each dose).

4.2 RADIATION THERAPY

4.2.1. IMRT reirradiation

IMRT reirradiation will be delivered in 60-66Gy in 30-33 once daily fractions over 6-6.5 weeks. Missed treatments due to holidays or logistic reasons can be compensated for by delivering an additional BID treatment during the week, OR treating on the Saturday or Sunday of that week, OR adding to the end of treatment.

4.2.2. Immobilization and Simulation

Patients must have an immobilization device (e.g. Aquaplast mask) made prior to treatment planning CT scan. Use of an immobilizing mouthpiece is optional as clinically indicated but preferred for any target of the oropharynx, or the hard palate/paranasal region. It is preferable to perform treatment planning CT scan with IV contrast if there are no medical contraindications to the use of contrast. The treatment planning CT scan must be performed with the immobilization device and in the treatment position. Slice thickness should be 0.3 cm or thinner.

4.2.3. Target Delineation

In setting of gross disease: In the setting of gross disease, the gross tumor volume (GTV) is defined as any tumor visible on imaging and/or physical exam. The Clinical Target Volume (CTV_66) is defined as the GTV plus an additional 3-5mm expansion that includes adjacent tissue at risk but respects normal tissue boundaries to tumor spread (e.g. bone, uninvolved muscle, etc). Generally an elective nodal volume will not be targeted. However, there are

several instances where an optional CTV_56.1 can be used to target initially uninvolved adjacent tissue for select patients with high risk of microscopic disease extent. Examples may include gross multifocal nodal disease, in which a CTV_56.1 can target an adjacent uninvolved nodal echelon to provide margin on the involved nodes, or disease that is grossly involving a cranial nerve for which a CTV_56.1 can be used to target the pathway of the nerve to the skull base. The Planning Target Volume (PTV_66) should be a 3mm isotropic expansion around CTV_66. If a CTV_56.1 is used, then a 3mm isotropic expansion around it will be generated to create the PTV_56.1. This volume should be given in 33 fractions.

In high risk postoperative setting

There is no gross tumor volume in the postoperative patient. However, the tumor/involved nodal bed should be included in the CTV_60Gy. Areas that are surgically dissected but uninvolved with tumor (e.g. elective neck dissection that is negative for disease) should generally not be targeted. However, there are several instances where an optional CTV_54 can be used to target adjacent tissue for select patients with high risk of microscopic disease extent. Examples may include pathologically proven multifocal nodal disease, in which a CTV_54 can target an adjacent uninvolved nodal echelon to provide margin on the involved nodes, or disease that is grossly involving a cranial nerve for which a CTV_54 can be used to target the pathway of the nerve to the skull base. The Planning Target Volume (PTV_60) should be a 3mm isotropic expansion around CTV_60. If a CTV_54 is used, then a 3mm isotropic expansion around it will be generated to create the PTV_54. This volume should be given in 30 fractions.

4.2.4. Critical Normal Structures

The normal tissue volume to be contoured will depend on the site of origin of the cancer. For all patients, they will include the brainstem, spinal cord, cochlea, mandible, constrictors, esophagus, trachea, oral cavity, glottis/supraglottic larynx, supraglottis, lips and parotid and submandibular salivary glands. Any of these structures surgically removed or absent can be ignored. The carotid artery should also be contoured. For tumors near the low neck, the brachial plexus must be contoured. For tumors near the skull base, the following should also be included: eyes, lenses, optic nerves, optic chiasm, and pituitary.

4.2.5. Treatment Planning and Delivery

Megavoltage energy photon beam irradiation is required. Inverse planning using intensity modulated RT or Cyberknife is mandatory. Static beam intensity modulation or volumetric arc based planning are acceptable for planning. Proton therapy is not allowed.

4.2.6. Image Guidance for IGRT

IGRT with daily conebeam CT is required. If a cone beam CT is not available, portal images or other on board imaging should be used daily. Region-of-Interest (ROI) or “clip box” for fusion should be set to encompass the PTV and adjacent spinal cord. When the skull base is targeted, the globes and optic nerves should routinely be included, if possible, for alignment purposes. Following the registration, the translational and (if the appropriate technology is available) rotational corrections should be applied to the treatment couch. If all the variances are less than 10 mm (this typically corresponds to one half of the usual PRV margin), the treatment can proceed with appropriate corrections; however, re-imaging is not mandatory. If one or more of the corrections are larger than 10 mm, the imaging must be repeated in addition to performing table/positioning adjustments. However, the use of numerous repeat IGRT studies should be avoided (see next section).

4.2.7. Definition of Normal Tissues/Organs at Risk (OARs)

NOTE: Only the parts of the normal tissues/organs at risk outside the PTVs will be considered for dose optimization purposes, except for the spinal cord and brainstem. Only those OAR that are in proximity to the treatment volume must be contoured. Contouring OAR that are far from the treated area and will receive negligible doses is unnecessary.

Spinal Cord: The cord begins at the cranial-cervical junction (ie, the top of the C1 vertebral body). Superior to this is brainstem and inferior to this is cord. The inferior border of the spinal cord volume will be defined at approximately T3-4 (ie, just below the lowest slice level that has PTV on it). The spinal cord shall be defined based on the treatment planning CT scan. In addition, however, a Planning Risk Volume (PRV) spinal cord shall be defined as: SpinalCord_05 = cord + 5 mm in all directions.

Brain Stem: The inferior most portion of the brainstem is at the cranial-cervical junction where it meets the spinal cord. For the purposes of this study, the superior most portion of the brainstem is approximately at the level of the top of the posterior clinoid. The brainstem shall be defined based on the treatment planning CT scan. In addition, however, a Planning Risk Volume (PRV) brainstem shall be defined as: Brainstem_03 = brainstem + 3 mm in all directions.

Globe of the eye: Self-explanatory

Optic Nerve: Self-explanatory

Optic Chiasm: Self-explanatory

Cochlea: Self-explanatory

Carotid Artery: This will include the carotid artery at the same level of the PTV plus an additional 2cm cranial and caudal to the level of the PTV. When the PTV is located above the carotid bifurcation, only the internal carotid artery (not the external branch) should be contoured.

Lips: The definition of lips is self-explanatory.

Oral Cavity: The oral cavity will be defined as a composite structure posterior to lips consisting of the anterior 1/2 to 2/3 of the oral tongue/floor of mouth, buccal mucosa, and superiorly the palate, and inferiorly to the plane containing the tip of the mandible.

Parotid Glands: Parotid glands will be defined in their entirety (superficial and deep lobes) based on the treatment planning CT scan.

Submandibular Glands: Submandibular glands will be defined in their entirety based on treatment planning CT scans.

Pharynx: This will be defined as the pharyngeal wall plus adjacent constrictor muscles deemed not to require treatment (external to PTVs). This extends from the superior constrictor region (level of the inferior pterygoid plates) to the cricopharyngeal inlet (level of the posterior cricoid cartilage).

Esophagus: This will be defined as the cervical or superior (S) esophagus, a tubular structure that starts at the bottom of pharynx (cricopharyngeal inlet) and extends to the thoracic inlet.

Glottic/Supraglottic Larynx: This will be defined as the glottic and supraglottic larynx, including the tip of the epiglottis, the aryepiglottic folds, arytenoids, false cords, and true cords, bounded by the thyroid cartilage laterally, anteriorly including the anterior edge of the pre-epiglottic fat, and posteriorly bounded by the anterior edge of the pharyngeal wall or the posterior edge of the arytenoid and/or cricoid cartilage.

Mandible: This includes the entire bony structure of the mandible from TMJ through the symphysis. It is recognized that for oral cavity cancers, this may overlap with PTVs.

Brachial Plexus: The defined ipsilateral brachial plexus originates from the spinal nerves exiting the neuroforaminal on the involved side from around C5 to T2. However, for the purposes of this protocol, only the major trunks of the brachial plexus will be contoured using the subclavian and axillary vessels as a surrogate for identifying the location of the brachial plexus. This neurovascular complex will be contoured starting proximally at the bifurcation of the brachiocephalic trunk into the jugular/subclavian veins (or carotid/subclavian arteries) and following along the route of the subclavian vein to the axillary vein ending after the neurovascular structures cross the second rib.

Unspecified Tissue Outside the Targets (E-PTV): This will be defined as tissue located between the skull base and thoracic inlet external to all PTVs and defined normal structures within the external contour of the patient.

Skin: This will be defined as an inner ring of tissue comprising the external skin and the tissue 3mm underneath it.

4.2.8. Dose Prescription

Doses to PTVs

All plans must be normalized such that 95% of the volume of the prescription PTV (PTV_66 for gross disease; PTV_60 for postoperative cases) is covered with the prescription dose (66Gy or 60Gy respectively). At 1 cc PTV_66 volume or PTV_60 volume on the DVH curve, the dose should not be > 110% of the prescribed dose. Ideally, less than 10% of PTV_66 or PTV_60 should receive 105% of the prescription dose (69.3Gy or 63.5Gy respectively). However, up to 20% of PTV_66 or PTV_60 can receive 105% of the prescription dose (69.3Gy or 63.5Gy) to allow for meeting dose constraints. For any volume of tissue outside the PTV(s) that has a size of 1 cc or more, the dose should not be > 66 Gy for definitive cases and >60Gy for postoperative cases.

Doses to Normal Structures

Spinal Cord: The cumulative dose to the spinal cord should not exceed 52Gy. In the event that the old plan is not available for review, the dose to the spinal cord should not exceed 10Gy and preferably be less than 8Gy to any volume in excess of 0.03 cc (approximately 3 mm x 3 mm x 3 mm).

In treatment planning, the spinal cord should be given the highest priority.

Spinal Cord PRV: The cumulative dose to the spinal cord PRV should not exceed 55Gy. In the event that the old plan is not available for review, the dose to the spinal cord should not exceed. The Spinal Cord PRV should not exceed 16Gy and ideally less than 14Gy.

Brainstem: The cumulative dose to the brainstem should ideally be limited to 0.03cc to 60Gy. However, if disease is in close proximity to brainstem and requires higher doses, especially if the original RT course exceeded this dose, this is acceptable. Ideally the max dose per fraction to the brainstem should be <1Gy per fraction. If the disease mandates exceeding this constraint, the patient should be informed of the risks of severe or life threatening toxicity. In the event that the old plan is not available for review the brainstem should not exceed 12Gy to any volume in excess of 0.03 cc (approximately 3 mm x 3 mm x 3 mm) and preferably should be less than 10Gy and the PRV/brainstem (brainstem +3mm) should be limited to 16Gy. However, if disease is in extremely close proximity to the brainstem, this may need to be exceeded. In this case, Ideally the max dose per fraction to the brainstem should be <1Gy

per fraction.

Coverage can be compromised to meet spinal cord and brainstem constraints as clinically indicated at the discretion of the treating radiation oncologist.

Optic Nerves and Chiasm: The cumulative dose to the optic structures should not exceed 55 Gy. In the event the that old plan is not available for review, the dose to the optic structures should not exceed a max dose of 10Gy to any volume greater than 0/03cc. In the rare event that a single optic nerve is involved with tumor, these constraints can be violated to achieve coverage of the tumor. However this would not apply to the optic chiasm or bilateral optic nerves.

Orbits: Should be limited to a cumulative max dose of 50Gy including previous radiation.

Lips: Reduce the dose as much as possible. The mean dose should be < 20 Gy when possible.

Oral Cavity: Reduce the dose as much as possible. The mean dose should be < 30 Gy when possible.

Parotid Glands (not targeted): In most cases, it will be easier to spare one parotid than the other. The treatment planning goal will be for this individual parotid gland to receive a mean dose of <26 Gy.

Submandibular gland (not targeted): If level Ib is not a target, aim to reduce mean contralateral submandibular gland to < 39 Gy.

OARpharynx/constrictors: Reduce the dose as much as possible. Some recommended (but not mandatory) treatment goals include: 1) No more than 33% of the OARpharynx exceeds 50Gy; 2) Mean dose < 45 Gy; 3) No more than 15% of the OARpharynx exceeds 60 Gy.

Cervical Esophagus: Reduce the dose as much as possible. Some recommended (but treatment goals include: Mean dose < 30 Gy.

Glottic and Supraglottic larynx (GSL): Reduce the dose as much as possible. The glottic larynx mean dose is recommended to be <25 Gy.

Mandible: Reduce the dose as much as possible. Hot spots within the mandible should be avoided. It is recommended that maximum dose within the mandible be < 66 Gy, except in areas overlapping PTV.

Unspecified Tissue Outside the Targets: No more than 1cc of unspecified tissue outside the targets can receive 66 Gy or more

Brachial Plexus: The dose to the plexus should be limited as much as possible. The plexus can never exceed 66Gy unless it is clinically involved with tumor. If it is uninvolved, it should be limited to <30Gy whenever possible.

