9. ADMINISTRATION, HANDLING OF DATA AND SAFETY MONITORING

9.1. PROTOCOL AMENDMENTS

Any changes to the protocol will be made in the form of an amendment and must be approved by the coordinating site IRB before implementation. Any modifications made to the protocol or informed consent document according to local requirements or any other reason may also require approval from sponsoring agencies.

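### Section 4.2.8 twice gives 105% of the 60 Gy postoperative prescription as 63.5 Gy; the correct value is 63.0 Gy

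*Combined protocol and SAP*

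**What the plan says.** Section 4.2.8 (Dose Prescription) requires every plan to be normalised so that 95% of the relevant PTV "is covered with the prescription dose (66Gy or 60Gy respectively"). The two volumes are identified as "PTV_66 for gross disease; PTV_60 for postoperative cases".

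The section then sets two levels of homogeneity limit, both tied to 105% of the prescription:

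- Preferred goal: "Ideally, less than 10% of PTV_66 or PTV_60 should receive 105% of the prescription dose (69.3Gy or 63.5Gy respectively").
- Outer allowance: "However, up to 20% of PTV_66 or PTV_60 can receive 105% of the prescription dose (69.3Gy or 63.5Gy) to allow for meeting dose constraints".

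A separate hot-spot cap applies at 1 cc of the PTV, where "the dose should not be > 110% of the prescribed dose". That cap is given only as a percentage.

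Section 4.2.3 (Target Delineation) agrees with the 60 Gy postoperative dose. It names the postoperative target volumes CTV_60 and PTV_60 and says "This volume should be given in 30 fractions". Sections 4.1 and 4.2.1 give an overall range of 60 to 66 Gy in 30 to 33 fractions, which is consistent with this.

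**The concern.** Each homogeneity sentence states its threshold twice, as a percentage and as an absolute dose. For PTV_66 the two agree. For PTV_60 they do not, because 63.5 Gy is more than 105% of 60 Gy.

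This is a working instruction to treatment planners, and the protocol does not say whether the percentage or the Gy value takes precedence. Section 3 states "Three sites will be involved", so a planner at one site could evaluate the dose-volume histogram at 63.0 Gy and a planner at another at 63.5 Gy, and they could reach different conclusions about the same postoperative plan. The printed Gy value errs in the permissive direction. These are also previously irradiated patients: inclusion criterion 8 in section 3.1.1 requires most of the target to have had at least 40 Gy already. The 20% sentence carries the same figure, so the outer allowance is affected as well as the softer goal.

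**Working it through.** **Inputs, all from section 4.2.8 unless noted**

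- Prescription for gross disease (PTV_66): 66 Gy
- Prescription for postoperative cases (PTV_60): 60 Gy
- Homogeneity threshold: 105% of prescription
- Printed thresholds, in both sentences: 69.3 Gy and 63.5 Gy
- Postoperative fractions: 30 (section 4.2.3)

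**Step 1. Reproduce the printed figures.** Threshold = 1.05 × prescription.

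| Volume | Prescription | 1.05 × prescription | Printed | Printed ÷ prescription |
|---|---|---|---|---|
| PTV_66 | 66 Gy | 69.3 Gy | 69.3 Gy | 105.0% |
| PTV_60 | 60 Gy | 63.0 Gy | 63.5 Gy | 105.83% |

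The PTV_66 value reproduces exactly. The PTV_60 value does not.

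**Step 2. Look for another explanation of 63.5 Gy.**

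- *Rounding.* The product 1.05 × 60 = 63.0 is exact, and the companion value is given to 0.1 Gy. No rounding step leads to 63.5.
- *A different prescription dose.* 63.5 ÷ 1.05 = 60.48 Gy, which is not a prescription dose anywhere in the protocol.
- *A different percentage.* 1.06 × 60 = 63.6 Gy and 1.10 × 60 = 66.0 Gy. Neither gives 63.5, and the text says 105%.
- *A text-extraction fault.* The value appears identically in two separate sentences of running prose, with nothing blacked out nearby. A misread digit is unlikely.

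**Step 3. Size of the discrepancy.**

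- Absolute: 63.5 − 63.0 = 0.5 Gy
- Relative to prescription: 0.5 ÷ 60 = 0.83%
- Per fraction: 63.5 ÷ 30 = 2.117 Gy against 63.0 ÷ 30 = 2.100 Gy, a difference of 0.017 Gy

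**Step 4. When it changes a judgement.** Let V63.0 and V63.5 be the percentages of PTV_60 receiving at least 63.0 Gy and at least 63.5 Gy. The two readings conflict in these cases:

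- Preferred goal: V63.0 is 10% or more while V63.5 is below 10%.
- Outer allowance: V63.0 is above 20% while V63.5 is 20% or less.

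In either case the plan passes on the printed Gy value and fails on the printed percentage.

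**Step 5. What is not affected.** The 110% cap at 1 cc has no Gy value printed beside it, so it stays at 1.10 × 60 = 66.0 Gy for PTV_60. The limit on dose outside the PTV, the cord and brainstem limits and the PTV_66 thresholds do not use 63.5 Gy. Nor do the sample size, the power statement or the Kaplan-Meier analysis of 1-year progression-free survival (PFS) in section 8.

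**The case against.** The arithmetic cannot be disputed; the case for leaving the text alone is that nothing depends on it. The correct percentage stands beside the wrong dose, and the correct 69.3 Gy shows that 105% is the rule, so a careful planner would resolve the conflict correctly. The 10% limit is only an ideal and the 20% limit is an allowance. The protocol attaches no deviation score, central plan review or eligibility consequence to either, and the monitoring provisions in section 9.5 deal with data, safety and site conduct rather than dosimetry. The other target-dose limits still apply, and the gap is only 0.5 Gy. That sites would actually plan differently is a possibility, since the protocol does not say which figure planners use.

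Most of this stands, and it is why the point is rated minor. Different practice between sites has not been shown. The objection does not make 63.5 Gy correct, and it offers no reading under which the two printed thresholds agree. A planning limit that contradicts itself is worth correcting when the correction needs no clinical judgement.

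**Conclusion.** The point holds. The postoperative dose in both homogeneity sentences of section 4.2.8 is wrong by 0.5 Gy: it should be 63.0 Gy (105.0% of 60 Gy) and is printed as 63.5 Gy (105.8%). The error loosens the limit slightly for dose inside PTV_60 and affects postoperative plans only.

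The conclusion rests on two readings of the text: that the postoperative prescription is 60 Gy, which sections 4.2.3 and 4.2.8 both state, and that 105% is the intended threshold, which the exact 69.3 Gy figure for PTV_66 supports. Severity is minor and confidence is high. No patient harm is inferred, and there is no consequence for the trial's statistical conclusions.

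**What to change.** In section 4.2.8, change 63.5 Gy to 63.0 Gy in the sentence setting the 10% goal and in the sentence setting the 20% allowance. Leave the 105% threshold, the 69.3 Gy figure and both volume limits as they are.

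The cost is one number in two places, with no new procedure, data item or analysis. Section 9.1 says "Any changes to the protocol will be made in the form of an amendment" and requires approval by the coordinating site's IRB before implementation. The correction does not warrant an amendment of its own and can go into the next one.
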